9.5 End of Study Definition

The study is planned over a 2 year period. Last visit of the last subject will take place by 18 months of the study start date i.e. all 12 participants would have had 2 bronchoscopies by 18 months. After this point we have planned 6 months for processing of clinical samples, molecular work, data analysis and interpretation.

10 Laboratories

10.1 Central/Local Laboratories

All the samples collected in this study will be processed in the laboratories of [name] and [name] [name] within King's College London at Guy's hospital campus.

10.2 Sample Collection/Labelling/Logging

Samples will be collected by the study direct care team. Samples will be immediately stored on ice or room temperature and labelled with patient code, visit number and the time of collection recorded on study worksheets. Each sample type will have specific SOPs and guidance on information that must be recorded at the appropriate environmental conditions to maintain sample integrity. The KCL

research team or delegated personnel who are appropriately trained will be contacted to inform them that the sample is ready for collection or that the sample is being delivered to the laboratory.

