We will integrate the spatial-associated RNA-seq datasets from bronchial biopsies (spatial transcriptomics, secondary objective 1) with bulk RNA-seq in BECs (secondary objective 2) and investigate changes in gene expression that relate to airways remodelling (e.g. genes encoding for structural proteins, integrins, extracellular matrix proteins etc.). We will focus on analysing non-stimulated BECs from secondary objective 2, pre- and post- benralizumab, which will show the changes in epithelium responses upon benralizumab treatment.

We will further analyse extracellular matrix (ECM) deposition and degradation in biopsies using antibodies directed against ECM proteins as well as chemical trichrome staining (Masson's) to visualise connective tissues (collagen), cells and smooth muscle. We will also establish transepithelial integrity/permeability assays employing different methods (e.g. dextran permeability through the epithelial barrier).

Where feasible, we will dissect larger bronchial biopsies and attempt to isolate other structural cells (smooth muscle and fibroblasts) for functional assays associated with inflammation and bronchoconstriction and examine: cell contractility, proliferation, migration, protein expression and cytokine production.

4. Determine the effect of benralizumab on small airway dysfunction using impulse oscillometry and MRI to measure the change in homogeneity of airways ventilation

Impulse oscillometry is a far more accurate measure of small airways airflow obstruction than standard spirometry, whilst ventilation assessed by inhaled gas MRI has been recently shown to be sensitive to anti-T2 therapies and can be used to objectively evaluate the functional consequence of clearing eosinophils from the airway lumen (Svenningsen et al. CHEST Oct 2020).

7 Study design & Flowchart

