7.1 Study Design

This is a prospective open label phase IV observational study

Primary Endpoint:

Change in the number / proportion of T2 related cellular populations in BAL including ILC2, Th2, alveolar macrophages, eosinophils and basophils pre- and post benralizumab (12 weeks).

Secondary Endpoints:

1. Change in cellular populations and gene expression of T2-related signalling pathways in bronchial biopsies pre- and post benralizumab
2. Change in type 1 & 3 interferon production and viral replication following infection of cultured BECs and alveolar macrophages with RV-16 and examine the response of cells to SARS-CoV-2 collected pre- and post- benralizumab.
3. Change in cellular populations and gene expression of remodelling-related pathways in bronchial biopsies pre- and post benralizumab
4. Change in airway oscillometry measures and MRI measures of ventilation pre- and post benralizumab.

Each recruited participant will be in the study for 3 months and will attend for 8 visits including screening and informed consent. Visits will include blood, breathing tests and bronchoscopy. Participants will undergo bronchoscopy twice in a 12 week period (pre- and 12 weeks post benralizumab treatment). Processing of biological samples and data from clinical measures will be mined throughout the study period of 24 months and also when patients revert to ongoing NHS clinical care that is standard for those on benralizumab treatment for their asthma.

Gantt Chart: The total study duration is 24 months.

Months	3	6	9	12	15	18	21	24
Ethics application and approval								
Patient recruitment, bronchoscopies and sample collection and laboratory procedures								
BEC and mac culture for anti-viral immunity								
BEC and Br biopsy Spatial transcriptomics								
Protein analysis								
Data analysis								
Manuscript(s) preparation								

Treatment Regimen:

Benralizumab will be commenced according to UK NICE severe asthma guidance with 30mg sc dosing every 4 weeks for first 3 doses, followed by every 8 weeks.

Design and patient flow:

- Visit 1: Consent, Enrollment and schedule of visit dates
- Visit 2: Day 1 Covid-19 test
- Visit 3: Day 2 Bronchoscopy
- Visit 4: Day 10 Subject receives benralizumab dose 1 (30mg subcutaneous injection)
- Visit 5: Day 38 Subject receives benralizumab dose 2 (30mg subcutaneous injection)
- Visit 6: Day 66 Subject receives benralizumab dose 3 (30mg subcutaneous injection)
- Visit 7: Day 83 Covid-19 test

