10.3 Sample Analysis Procedures

The aim is to study the influence of benralizumab on structural and inflammatory airway cells in patients with severe eosinophilic asthma.

Our primary outcome measure is:

The change in the number / proportion and/or activation status of Type-2 related cellular populations in samples derived from bronchoscopy including bronchial biopsies, bronchoalveolar lavage (BAL) and bronchial brushings. These cells include ILC2, Th2, alveolar macrophages, epithelial cells, eosinophils and basophils pre- and post- 12 weeks of benralizumab using molecular techniques.

Secondary Endpoints:

To investigate the following before and after completing treatment with 12 weeks of benralizumab.

1. Changes in epithelial barrier integrity using cell biology methods such as transepithelial resistance or barrier permeability.
2. Changes in epithelial antiviral responses in untreated vs respiratory virus-infected cells including rhinovirus-16 and SARS-CoV-2 using protein and nucleic acid analyses.
3. Changes in the antiviral responses of alveolar macrophages to rhinovirus-16 or other respiratory virus infection using protein and nucleic acid analyses.
4. Changes in epithelial responses to cytokines/chemokines and/or exposure to other cell types (co-cultures).
5. Changes in airway remodelling by histological examination.
6. Changes in the profile and function of isolated structural cells (such as airway smooth muscle and epithelial cells but not restricted to) dissected from larger biopsies by molecular and cellular methods.
7. To evaluate the impact on peripheral airways by obtaining bronchoalveolar lavage (BAL) and performing nucleic acid and protein analyses
8. Peripheral airway dysfunction using tests such as impulse oscillometry but not restricted to.
9. Change in FeNO levels.

Study procedures- Clinical Assessment

The CRF will be completed and include clinical details about asthma and other relevant medical conditions and medications.

Spirometry

Spirometry will be conducted in hospital using a spirometer conforming to ATS/ERS standards as specified by the manufacturer's instructions. FEV1 (L), FVC (L), FEV1/FVC ratio, FEF25-75 (% of predicted value) and PEF (L/min) will be recorded. FEV1, FVC and PEF will be documented as both absolute values and as a percentage of the predicted value.

Oscillometry

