Oscillometry is a non-invasive measure of pulmonary resistance and reactance. By measuring oscillating pressures/flow signals of moving air within the lungs, when generated at different frequencies, it provides measures of airway mechanics from different lung regions. Generally lower frequencies, in particular frequency dependent changes in resistance between 5 and 20 Hz and capacitive reactance at 5 Hz are thought to reflect changes arising in the more distal airways. Oscillometry will be performed pre- and post-bronchodilator.

Fractional nitric oxide (FeNO)

FeNO is a surrogate marker of T2-airway inflammation. FeNO will be measured using a NIOX VERO device, as specified by the manufacturer's instructions. This includes collection by controlled exhalation at the recommended controlled expiratory flow rate of 50ml/s for greater than 6 seconds.

Blood sampling

Blood will be collected for routine full blood count (including blood eosinophil and basophils), biochemistry and coagulation measurements pre-bronchoscopy. In addition plasma/ serum will be stored for proteomic/nucleic acid analyses.

Bronchoscopy

Bronchoscopy will be conducted according to established guidelines, and will be performed by respiratory physicians experienced in bronchoscopy. Participants will receive nebulised salbutamol (2.5mg) and ipratropium bromide (500mcg) prior to the procedure. Local anaesthesia will be achieved with gel applied to the nasal passages and lignocaine spray to the throat, soft palate and pharynx. Intravenous sedation using midazolam (maximum 5 mg) and alfentanil (maximum 500 mcg) will be given to achieve conscious sedation. A flexible bronchoscope will then be passed either through the nose or mouth into the lungs with additional lignocaine spray being applied to prevent coughing.

- i) Bronchial brushings will be performed using single-use brushes. Up to a total of 6 brushes will be taken.

- ii) Bronchial biopsies will be performed from the lower and middle lobes using single use forceps. Up to 6 evaluable biopsies will be taken.
- iii) Bronchoalveolar lavage (BAL): the bronchoscope will be inserted in a sub-segmental bronchi and 60ml aliquots of pre-warmed 0.9% saline will be instilled followed by gentle suction to recover lining fluid. This will be repeated up to 3 times.

At the first bronchoscopy (Visit 3) samples will be collected from the right side of the lung and at second bronchoscopy (Visit 8) samples will be taken from the left side.

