10.6 Sample Receipt/Chain of Custody/Accountability

Firstly, a materials transfer agreement will be in place between the GSTT and KCL site for sample transfer and chain of custody processes. Laboratory SOPs are in place to meet GCLP and HTA compliance. Sample receipt and processing worksheets will be in place for each sample type to record the patient code number, visit number, date, time and condition of the samples upon arrival to the laboratory. Sample labelling will be maintained throughout the processing and storing procedure.

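### The laboratory can see from the visit number which bronchoscopy samples are post-benralizumab, and the protocol provides no masked reading for the reader-dependent endpoints

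*Protocol*

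**What the plan says.** **Design.** Section 7.1 states: "This is a prospective open label phase IV observational study". There is one group, and the main comparison is before against after benralizumab. The primary endpoint there is "Change in the number / proportion of T2 related cellular populations in BAL including ILC2, Th2, alveolar macrophages, eosinophils and basophils" before treatment and at 12 weeks. Section 6 names CyTOF as the assay for BAL cells.

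**Labelling.** Under section 10.2 samples are "labelled with patient code, visit number and the time of collection recorded on study worksheets". Section 10.6 adds: "Sample receipt and processing worksheets will be in place for each sample type to record the patient code number, visit number, date, time" and condition on arrival. It then states: "Sample labelling will be maintained throughout the processing and storing procedure".

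**When samples are taken.** The flowchart in 7.2 shows bronchoscopy at Visits 3 and 8 only, with the three benralizumab doses at Visits 4, 5 and 6. Section 10.3 says: "At the first bronchoscopy (Visit 3) samples will be collected from the right side of the lung and at second bronchoscopy (Visit 8"), with the left side used on the second occasion.

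**Steps that involve reading.** Secondary objective 3 in section 6 examines extracellular matrix in biopsies "using antibodies directed against ECM proteins as well as chemical trichrome staining (Masson's) to visualise connective tissues (collagen), cells and smooth muscle". Section 10.3 lists "Changes in airway remodelling by histological examination" among its secondary endpoints. Secondary objective 1 uses immunofluorescence to confirm markers found by spatial transcriptomics.

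**Text that points the other way.** Sections 10.5 and 13.2 say that specimens and stored samples are identified by a study number and nothing else. The stated reason is participant confidentiality.

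**The concern.** Treatment cannot be masked in this design, but the reading of samples can be. For bronchoscopy samples the visit number has two possible values, one before and one after treatment, so anyone who sees it knows the condition. The synopsis and section 10.1 place processing and analysis with the study team and its collaborators. The hypothesis in section 5 is directional: it expects T2 inflammation to be dampened beyond the loss of eosinophils.

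Without a control group, the before/after difference is the whole result. If knowledge of the visit moves a population boundary or a histology score slightly in the expected direction, that movement is counted as a treatment effect. Section 14.2 makes all analyses paired, which removes differences between patients. It does not remove a shift that has the same sign in every patient. A later analysis cannot separate the two once the readings exist.

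**Working it through.** **1. Does the laboratory receive the visit number?** Section 10.2 can be read two ways: the visit number is on the sample label, or it is only on the worksheet. Under either reading, section 10.6 has it recorded again at laboratory receipt and processing for each sample type. The laboratory has it both ways.

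**2. Does the visit number reveal treatment status?** Yes for BAL, biopsies and brushings. Visit 3 precedes the first dose and Visit 8 follows the third. Lung side carries the same information (right before, left after), and so does the collection date.

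**3. Does any section mask the reader?** No section mentions masked or blinded reading, re-coding before assay, or random ordering of paired samples. Pseudonymisation in 10.5 and 13.2 hides the person. Taken literally, its study-number-only rule conflicts with 10.2 and 10.6, but it sets no masking.

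**4. Which endpoints are exposed?** Assignment of BAL cells to populations (primary), trichrome and matrix histology, and immunofluorescence. RNA-seq, spatial transcriptomics, oscillometry and FeNO are mainly pipeline or instrument outputs and are little affected.

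**5. How large could the effect be?** The protocol gives no reader error, SD or significance level for these endpoints, so there is no figure of its own to reproduce. Its number of patients, n = 12 (14.1), is used below. The rest is assumed: no true effect, an uncorrected two-sided 5% paired t-test, and a constant reader shift of d standard deviations of the paired difference.

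- Mean paired difference in SD units = true effect + d = 0 + d. The bias is d whatever the sample size.
- The test statistic follows a noncentral t with 12 − 1 = 11 degrees of freedom and noncentrality d × √12 = 3.464 × d.
- The critical value is 2.201. Rejection probability = P(|T| > 2.201).

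| Assumed shift d | Noncentrality, 12 pairs | False-positive rate, 12 pairs | Same, 10 pairs |
|---|---|---|---|
| 0 | 0 | 5.0% | 5.0% |
| 0.1 | 0.346 | 6.2% | 5.9% |
| 0.2 | 0.693 | 9.7% | 8.8% |
| 0.3 | 1.039 | 15.8% | 13.6% |
| 0.5 | 1.732 | 35.3% | 29.3% |

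The last column uses 9 degrees of freedom and d × √10, in case only 10 pairs can be read.

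**The case against.** The strongest case on the other side has five parts.

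- **Custody labels are not reading rules.** Sections 10.2 and 10.6 exist for traceability. A tube that shows its visit number does not stop anyone from re-coding a slide or a data file before it is read. This stands. A reader might infer that the labelling rule itself rules out masking, or that each reader knows the condition at the moment of reading. The protocol supports neither: it shows that the laboratory holds the information and that no masking step is stated. The sample-type SOPs mentioned in 10.2 and any statistical analysis plan are not shown, and either could contain such a step.
- **Sections 10.5 and 13.2 say otherwise.** They do, and for that reason it cannot be said without qualification that every sample bears its visit number throughout. But their purpose is confidentiality, and 10.6 still gives the laboratory the visit number.
- **Few endpoints need judgement.** This stands for most of the secondary endpoints in 7.1. It does not stand for the primary endpoint, where cells must be assigned to populations from a marker panel. The protocol does not describe how that assignment is made.
- **The magnitude is hypothetical.** It is. At 0.1 SD the error rate is close to nominal. Section 14.2 attaches t-tests to clinical outcomes and requires a multiplicity correction where several variables are compared, so the uncorrected test is not the stated plan for several BAL populations. Correction would lower the rates in the table but would not remove the bias in the estimate.
- **Masking will be imperfect.** Eosinophil loss can reveal a post-treatment sample, and staff who receive samples about 12 weeks apart can infer their order. Both are true. Masking at the reading step still protects histology and the populations other than eosinophils, where the study looks for its new effects.

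**Conclusion.** The point holds in a limited form. Under the protocol as written, the laboratory can tell pre-treatment from post-treatment bronchoscopy samples, and nothing provides for readings made without that knowledge. This matters for CyTOF population assignment in the primary endpoint, for histology and for immunofluorescence, and little elsewhere. The study-number-only statements in 10.5 and 13.2 conflict with 10.2 and 10.6 and need reconciling, but they do not close the gap.

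The documents do not show that bias will occur or how large it would be. The false-positive rates of about 6% to 35% rest entirely on assumed shifts of 0.1 to 0.5 SD, no true effect, 12 pairs and an uncorrected 5% t-test. The firm conclusion is qualitative: a same-direction reader shift would go undiluted into the only comparison that the study makes. The change should be made before any reading starts.

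**What to change.** Keep the visit number on tubes and custody worksheets. Removing it there is unnecessary and would add a risk of mix-ups in a design that depends on correct pairing. Add to sections 10.3 and 10.6:

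1. Before reading, existing staff who do not perform that reading re-code slides, images and CyTOF files with random codes. The codes withhold visit, collection date and time, and lung side.
2. Pre and post CyTOF files are gated with one template, fixed on the pooled data.
3. Histology and immunofluorescence are read under code.
4. The link to patient and visit is released only after the readings are locked. Two random codes per patient keep the pairing recoverable.

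Reconcile the study-number-only wording in 10.5 and 13.2 with 10.2 and 10.6, so that it is clear what is on the tube, what is on the worksheet and what the reader sees. If an SOP already contains these steps, a reference to it is enough.

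The cost is protocol wording, a code list and one re-coding step by existing staff, with no added patient procedure and no extra reader. Masking will remain incomplete where eosinophil loss reveals the visit, and the report should say so.

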10.3 Sample Analysis Procedures

The aim is to study the influence of benralizumab on structural and inflammatory airway cells in patients with severe eosinophilic asthma.

Our primary outcome measure is:

The change in the number / proportion and/or activation status of Type-2 related cellular populations in samples derived from bronchoscopy including bronchial biopsies, bronchoalveolar lavage (BAL) and bronchial brushings. These cells include ILC2, Th2, alveolar macrophages, epithelial cells, eosinophils and basophils pre- and post- 12 weeks of benralizumab using molecular techniques.

Secondary Endpoints:

To investigate the following before and after completing treatment with 12 weeks of benralizumab.

1. Changes in epithelial barrier integrity using cell biology methods such as transepithelial resistance or barrier permeability.
2. Changes in epithelial antiviral responses in untreated vs respiratory virus-infected cells including rhinovirus-16 and SARS-CoV-2 using protein and nucleic acid analyses.
3. Changes in the antiviral responses of alveolar macrophages to rhinovirus-16 or other respiratory virus infection using protein and nucleic acid analyses.
4. Changes in epithelial responses to cytokines/chemokines and/or exposure to other cell types (co-cultures).
5. Changes in airway remodelling by histological examination.
6. Changes in the profile and function of isolated structural cells (such as airway smooth muscle and epithelial cells but not restricted to) dissected from larger biopsies by molecular and cellular methods.
7. To evaluate the impact on peripheral airways by obtaining bronchoalveolar lavage (BAL) and performing nucleic acid and protein analyses
8. Peripheral airway dysfunction using tests such as impulse oscillometry but not restricted to.
9. Change in FeNO levels.

Study procedures- Clinical Assessment

The CRF will be completed and include clinical details about asthma and other relevant medical conditions and medications.

Spirometry

Spirometry will be conducted in hospital using a spirometer conforming to ATS/ERS standards as specified by the manufacturer's instructions. FEV1 (L), FVC (L), FEV1/FVC ratio, FEF25-75 (% of predicted value) and PEF (L/min) will be recorded. FEV1, FVC and PEF will be documented as both absolute values and as a percentage of the predicted value.

Oscillometry

Oscillometry is a non-invasive measure of pulmonary resistance and reactance. By measuring oscillating pressures/flow signals of moving air within the lungs, when generated at different frequencies, it provides measures of airway mechanics from different lung regions. Generally lower frequencies, in particular frequency dependent changes in resistance between 5 and 20 Hz and capacitive reactance at 5 Hz are thought to reflect changes arising in the more distal airways. Oscillometry will be performed pre- and post-bronchodilator.

Fractional nitric oxide (FeNO)

FeNO is a surrogate marker of T2-airway inflammation. FeNO will be measured using a NIOX VERO device, as specified by the manufacturer's instructions. This includes collection by controlled exhalation at the recommended controlled expiratory flow rate of 50ml/s for greater than 6 seconds.

Blood sampling

Blood will be collected for routine full blood count (including blood eosinophil and basophils), biochemistry and coagulation measurements pre-bronchoscopy. In addition plasma/ serum will be stored for proteomic/nucleic acid analyses.

Bronchoscopy

Bronchoscopy will be conducted according to established guidelines, and will be performed by respiratory physicians experienced in bronchoscopy. Participants will receive nebulised salbutamol (2.5mg) and ipratropium bromide (500mcg) prior to the procedure. Local anaesthesia will be achieved with gel applied to the nasal passages and lignocaine spray to the throat, soft palate and pharynx. Intravenous sedation using midazolam (maximum 5 mg) and alfentanil (maximum 500 mcg) will be given to achieve conscious sedation. A flexible bronchoscope will then be passed either through the nose or mouth into the lungs with additional lignocaine spray being applied to prevent coughing.

- i) Bronchial brushings will be performed using single-use brushes. Up to a total of 6 brushes will be taken.

- ii) Bronchial biopsies will be performed from the lower and middle lobes using single use forceps. Up to 6 evaluable biopsies will be taken.
- iii) Bronchoalveolar lavage (BAL): the bronchoscope will be inserted in a sub-segmental bronchi and 60ml aliquots of pre-warmed 0.9% saline will be instilled followed by gentle suction to recover lining fluid. This will be repeated up to 3 times.

At the first bronchoscopy (Visit 3) samples will be collected from the right side of the lung and at second bronchoscopy (Visit 8) samples will be taken from the left side.

The bronchoscopy will be rescheduled if the patient has had an asthma exacerbation in the preceding 6 weeks.

Study Procedures- molecular

Epithelial brushes processing

Two brushings per patient will be stored at -80°C in RNA stabilising agent for future analysis. Four brushings will be processed for basal airway epithelial isolation by culturing in selective medium as previously described. Cultured cells, which are mainly basal epithelium, will be processed and infected/non infected with respiratory viruses including (but not restricted to) rhinovirus and SARS-CoV-2 to assess genome-wide changes, both at baseline and in their antiviral response upon benralizumab treatment. We will first set up time courses of 8, 24 and 48h given that the responses to rhinovirus and SARS-CoV-2 in bronchial epithelium differs in its dynamics, and sequence a single time point that is appropriate. We will keep RNA samples for all time points assessed for future validation purposes, together with supernatants to enable analysis of cellular mediators.

Cells infected/uninfected with virus will be subjected to RNA-seq after treatment. Top candidates based on statistical and biological significance will be validated by qPCR; western blotting/ELISA or other protein detection approaches. In the validation experiments we will also employ UV-inactivated virus as additional control. Cell culture supernatants will be collected to assess virus titres and RNA, as well as for future protein expression analyses. Cell lysates will also be stored for future protein level assessment using different platforms (proteomics; western blotting; ELISA or similar such as Luminex, O-link, etc.). Same passage cells will also be frozen for future analyses and exploratory studies detailed above.

Endobronchial biopsies

Up to 6 biopsies will be obtained:

Spatial transcriptomics: the optimal conditions of hybridization and staining will be firstly titrated in the lab using currently existing biopsy samples, to determine optimal conditions to process all samples. Biopsies will be fixed and both cryopreserved (snap frozen) as well as processed in paraffin wax for histological applications such as Visium Spatial Gene Expression protocols.

Bronchoalveolar lavage processing

An aliquot of bronchoalveolar lavage (BAL) will be stored for microbiome analysis. The BAL will then be spun to obtain cell pellets. Supernatant will be aliquoted for future analyses including microbiome, RNA and protein expression.

An aliquot of at least 1 million cells will be frozen for future analyses. Cells will be plated to isolate alveolar macrophages as previously described. Purified alveolar macrophages will be infected/uninfected with respiratory viruses (including but not restricted to rhinovirus and SARS-CoV-2), processed for RNA and protein measurements and stored at -80C for future analyses. Supernatants will also be collected for future analyses.

Blood samples

Blood samples will be spun on the same day of extraction. Serum/plasma will be frozen for proteomics/nucleic acid analysis. An aliquot of whole blood cells will be stored in an RNA stabilising agent and aliquots of whole blood cells and peripheral blood mononuclear cells obtained by gradient centrifugation will also be frozen in freezing medium for future analyses.

